8.2.3.2. Adverse Events

- **Adverse events**

The number and proportion of patients with adverse events will be tabulated by SOC and PT.

- **Adverse events by serious/non-serious**

The number and proportion of patients with serious adverse events will be tabulated by SOC and PT. The same tabulation will be performed for non-serious adverse events.

8.2.3.3. Other Endpoints

Not applicable.

8.2.3.4. Subgroup Analysis

The number and proportion of patients who experienced at least one adverse reaction will be tabulated for each factor specified in Section 5.4. To evaluate the relationship between patient background factors and the development of adverse reactions, the analysis based on risk ratio and risk difference specified in Section 8.1.3 will be performed. For subgroups with

risk ratio ≥ 2 or ≤ 0.5 , the number and proportion of patients who experienced adverse reaction will be summarized for each factors, using SOCs and PTs. It should be noted that if adverse reactions developed in less than a total of 10 patients, the risk ratio and risk difference will not be calculated, although the proportion will be presented for each factors.

The number and proportion of patients who experienced adverse reaction will be summarized by maximum number of daily doses, based on SOCs and PTs. Similarly, the number and proportion of patients who experienced serious adverse reaction will be summarized by maximum number of daily doses.

Listing of adverse reactions that developed in contraindicated patients will be tabulated. In addition, the number and proportion of those contraindicated patients who experienced adverse reactions will be tabulated by SOC and PT, as necessary.

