6. RESEARCH QUESTION AND OBJECTIVES

This study will be conducted to investigate the safety and effectiveness of this drug in daily clinical practice. Additionally, it is intended to assess the following:

- Adverse reactions unexpected from precautions, and
- Occurrence of adverse reactions under actual clinical settings

"Central nervous system disorder" also will be confirmed for the tendency of adverse reactions under actual clinical settings.

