7.5. Study size

7.5.1. Planned sample size

100 patients (for safety analysis)

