7.5.2. Rationale for sample size

The target sample size was set to be 100 patients, which should enable to detect, at 95% probability, an adverse reaction of which the true incidence rate is 3% in reference to adverse reaction of the least incidence in a clinical study of this drug (Study A6831005). This sample size should enable to confirm whether the types and incidence of adverse reaction related to this

drug used for diseases other than intra-abdominal infection, and pelvic inflammatory disease and other related diseases (hereinafter referred to as "PID") that were targeted in the clinical study would be similar to those occurred in Study A6831005.

Events specified as important identified risks or important potential risks in the Risk Management Plan (RMP) may not have a high incidence, and thus, may not detect sufficient information only from the drug use investigation; nonetheless, such an event collected in the drug use investigation should be investigated within the framework of the drug use investigation. Moreover, these events should also be monitored through the routine pharmacovigilance activities.

The sample size of 100 patients are expected to enable accumulating data on the number of patients at the level similar to the clinical study in terms of clinical response rate of this drug for diseases other than intra-abdominal infection and PID that were targeted in the clinical study and also in terms of clinical response rate in subgroup analysis by each major indication; which should enable verification whether the effectiveness under actual clinical settings is similar to the results of the clinical study.

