| | | | 
into dose escalation and overdose, and a definition of overdose was added.
 
6.2.3. Eradication/Persistence of Each Pathogenic Organism/Strain
 
 - A description for the eradication/persistence was added for the case of pathogenic organism/bacteria being Eubacterium spp. or Entamoeba histolytica. 
8.1.3. Analysis of Binary Data
 
 - A plan of calculating risk difference and its 95% confidence interval was added. 
8.2.1. Overview of Patients
 
 - Added specific categories of discontinuation time for listing of discontinuations and dropouts. - Patients who are to be excluded from the microbiological response analysis set were excluded from the planned listing of excluded patients. 
8.2.2. Patient Background and Treatment History of Anaemetro
 
 - The plan of summarizing data by the experience of 4-times-a-day dosing was changed to by maximum number of daily doses. - Changes were made for exposure factors (duration of treatment, number of daily doses, and dose per single dose). - Dose escalation and overdose were added to the set of exposure factors. - Considering the existence of patients who were off treatment for a long period, the treatment duration was redefined as an actual treatment duration excluding the period during which Anaemetro is suspended. 
8.2.3.1. Adverse Reactions
 
The categories for time to first development were changed.
 
8.2.3.4. Subgroup Analysis
 
 - Clarified that the subgroup analysis will be performed in terms of risk ratio and risk difference. Specified that calculation of the number and proportion of patients with adverse reactions by subgroup based on SOCs and PTs will only be performed for subgroups with risk ratio ≥ 2 or ≤ 0.5. - Considering the limited number of patients with AEs, the plan of calculating the risk ratio and risk difference for |

| Version | Date | Author(s) | Summary of Changes/Comments |
|---------|------|-----------|--|

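### For most subgroup factors, adverse reactions are tabulated by type only when the any-reaction risk ratio is at least 2 or at most 0.5, a rule that usually misses an excess of one reaction type and in small numbers often fires by chance

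*SAP*

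**What the plan says.** SAP 8.2.3.4 sets the subgroup endpoint: "The number and proportion of patients who experienced at least one adverse reaction will be tabulated for each factor specified in Section 5.4". Risk ratios and risk differences follow, calculated as in SAP 8.1.3, which also gives 95% confidence intervals. For subgroups with "risk ratio ≥ 2 or ≤ 0.5", the section adds that "the number and proportion of patients who experienced adverse reaction will be summarized for each factors, using SOCs and PTs". The confidence interval plays no part in this condition. The SAP's own change log describes the rule in the same restrictive sense: the breakdown "will only be performed for subgroups with risk ratio ≥ 2 or ≤ 0.5".

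A floor applies as well: "if adverse reactions developed in less than a total of 10 patients, the risk ratio and risk difference will not be calculated". Overall proportions per factor are still shown below the floor, but without a ratio the breakdown by system organ class (SOC) and preferred term (PT) has no trigger.

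The SAP makes these provisions outside the trigger:
- **Maximum number of daily doses** gets an SOC/PT table whatever the ratio (8.2.3.4).
- **Contraindicated patients** get a listing and, if judged necessary, an SOC/PT table (8.2.3.4).
- **Central nervous system (CNS) disorder:** patient background is tabulated by its presence or absence (8.2.2), and the patients are listed (section 9).
- **Hepatic dysfunction, renal dysfunction and elderly patients:** those with adverse reactions are listed (section 9).
- **The most frequent safety specification items:** background and concomitant medications are listed for the patients affected (8.2.3.1).

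**The concern.** SAP 8.2.3.4 gives its purpose as evaluating how patient background relates to the development of adverse reactions, and Protocol 7.7 plans to evaluate factors affecting their occurrence as necessary. A factor often matters for one kind of reaction and not for reactions in general. A rule that acts on the total can therefore stay silent in the case of most interest. Because it looks only at a point estimate, in about 100 patients it can also fire on sampling variation alone.

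The report could then show reaction profiles for factors selected partly by chance and omit the profile of a factor with a real, type-specific difference. The factors exposed to this are diagnosis, prior and concomitant infection medication, dose escalation, overdose and pregnancy. Hepatic dysfunction, renal dysfunction and age are exposed less, because they have line listings.

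**Working it through.** **Inputs from the documents.** N = 100 for safety (Protocol 7.5.1). The sample size rests on detecting, "at 95% probability, an adverse reaction of which the true incidence rate is 3" per cent (Protocol 7.5.2). The trigger is a risk ratio of at least 2 or at most 0.5 for any reaction, and the floor is 10 reacting patients (SAP 8.2.3.4).

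**Assumptions, because the documents do not give them.** The total number of reacting patients T, the subgroup size n, the rate q of all other reactions, and the size k of the excess. Ranges are shown.

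**1. The plan's own figure.** P(at least one case) = 1 − 0.97^100 = 0.952. The stated 95% reproduces.

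**2. Excess of one reaction type.** Let one reaction have 3% incidence in the reference group and k × 3% in the subgroup. Other reactions occur independently at rate q in both groups.
- Reference any-reaction rate: 1 − (1 − q)(0.97).
- Subgroup any-reaction rate: 1 − (1 − q)(1 − 0.03k).
- Largest ratio in the range (q = 0.10, k = 5): (1 − 0.90 × 0.85) / (1 − 0.90 × 0.97) = 0.235 / 0.127 = 1.85.
- Smallest ratio in the range (q = 0.30, k = 3): (1 − 0.70 × 0.91) / (1 − 0.70 × 0.97) = 0.363 / 0.321 = 1.13.

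The true any-reaction ratio is below 2 throughout. Exact enumeration of the two binomials, requiring T ≥ 10 and an observed ratio of at least 2 or at most 0.5, gives the probability that the table is **not** printed:

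| Other reactions q | n = 20, k = 3 / 5 | n = 30, k = 3 / 5 | n = 50, k = 3 / 5 |
|---|---|---|---|
| 10% | 67% / 53% | 73% / 56% | 71% / 52% |
| 20% | 83% / 77% | 89% / 82% | 88% / 81% |
| 30% | 93% / 92% | 96% / 95% | 96% / 94% |

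The range is 52 to 96%. No offsetting deficit in other reactions is needed.

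**3. Chance triggers with no true association.** Given T reacting patients among 100, the number a in a subgroup of n is hypergeometric. For T = 15 and n = 20, the ratio is (a/20) / ((15 − a)/80) = 4a/(15 − a). It is at least 2 when a ≥ 5 and at most 0.5 when a ≤ 1, so P = 0.147 + 0.145 = 0.292. In the table, a zero in the subgroup counts as ratio 0 and a zero in the reference group as a ratio above 2.

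| T | n = 10 | n = 15 | n = 20 | n = 30 | n = 50 |
|---|---|---|---|---|---|
| 10 | 59% | 35% | 47% | 27% | 32% |
| 15 | 35% | 46% | 29% | 22% | 26% |
| 20 | 47% | 19% | 24% | 11% | 8% |
| 30 | 17% | 14% | 11% | 6% | 5% |
| 40 | 16% | 8% | 4% | 2% | 1% |

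SAP Appendix 2 lists 13 contrasts. Four concern number of daily doses, which is broken down regardless, so 13 − 4 = 9 depend on the trigger. At T = 15 the expected number of chance triggers is 9 × 0.22 = 2.0 to 9 × 0.46 = 4.1. This treats every contrast as drawn from all 100 patients, which is a simplification for the three pairwise diagnosis rows.

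**4. The floor.** P(T < 10) for Binomial(100, p) is 97%, 45%, 5.5% and 0.2% at overall reaction rates of 5%, 10%, 15% and 20%. Below the floor, no ratio-dependent factor can be broken down.

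**The case against.** The best defence is that nothing is decided by this rule. SAP 4.1 calls the tests exploratory and 4.2 has no decision rule. A trigger only prints a descriptive table, so a table printed by chance does little harm in itself. With 10 to 20 reacting patients, SOC/PT cells would mostly hold 0 to 2 patients, the line listings can be read in full, and 8.2.3.5 allows further exploratory work. All of this stands and limits the weight of the point. It does not supply a comparison: the listings give no comparator proportions by reaction type, and the exploratory work is optional.

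A reader might infer that an excess of CNS reactions would be hidden, contrary to the Protocol section 6 aim that CNS disorder "also will be confirmed for the tendency of adverse reactions under actual clinical settings". The documents do not support that. SAP 8.2.2 tabulates background by CNS disorder without any ratio condition, covering age group, diagnosis, hepatic and renal dysfunction, and prior and concomitant infection medication. For those factors this is the same two-by-two table read the other way. Dose escalation and overdose are not in that background list, so the cover is large but not complete.

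A reader might also infer that false triggers are frequent whatever the data. That depends on the reaction rate. At 30 reacting patients the chance is 5 to 17%, at 40 it is 1 to 2% for subgroups of 30 to 50, and below 10 it is nil. Some chance triggers are also low ratios: at 15 reacting patients, a chance ratio of 2 or more occurs in 11 to 17%.

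Appendix 1 heads its example with a single event name, which could suggest event-specific ratios. The text of 8.2.3.4 nevertheless defines the analysis on at least one adverse reaction.

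**Conclusion.** The point holds as one of selective and incomplete exploratory reporting; it is not an error-rate breach. The main weakness is that the trigger acts on the total. Under the stated assumptions, a 3- to 5-fold excess of one 3% reaction leaves the any-reaction ratio at 1.13 to 1.85, and the breakdown is absent with probability 52 to 96%. The secondary weakness is lack of precision: chance triggers of 27 to 59%, 22 to 46%, 8 to 47% and 5 to 17% at 10, 15, 20 and 30 reacting patients, for subgroups of 10 to 50. Over the nine affected Appendix 2 contrasts, that is roughly 2 to 4 at 15 reacting patients.

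The reaction rate, subgroup sizes and size of the excess are assumptions. That the rule uses the total, ignores the confidence interval and cannot fire below 10 reacting patients comes directly from the SAP. The gap is mainly in non-CNS reaction types.

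**What to change.** In SAP 8.2.3.4:
- Delete the condition on a ratio of at least 2 or at most 0.5.
- For every factor in SAP 5.4, tabulate the number and proportion of patients with adverse reactions by SOC and PT, and by safety specification item, whatever the overall ratio or number of reacting patients. The section already does this by SOC and PT for maximum number of daily doses.
- Keep the 10-patient rule only for calculating risk ratios and risk differences.
- State that the ratio is for any adverse reaction, so that the single-event heading in Appendix 1 is not read otherwise.

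The cost is SAP wording and roughly ten extra tables from the same program, some of them sparse. No new data are needed.

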8.2.3.5. Exploratory Analysis

Additional exploratory analysis may be performed, as necessary. Among those exploratory analysis, only those that resulted in important interpretations will be reported.

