7.7. Data analysis

The details of methods of analysis on data collected in this study shall be described in the statistical analysis plan (SAP) to be separately prepared.

- Definition of analysis set

The safety analysis set shall include patients for whom the registration in this study and administration of this drug have been confirmed.

Two analysis sets, which are clinically-evaluable analysis set and microbiological analysis set shall be defined as the effectiveness analysis set. The clinically-evaluable analysis set includes patients who were confirmed to conduct the clinical evaluation in the safety analysis set. The microbiological analysis set includes patients for whom microbiological response was assessed in the clinically-evaluable analysis set.

- Methods of analysis

(1) Analysis for safety evaluation

The incidence of adverse reactions will be calculated for each event. Also, the factors affecting the occurrence of adverse reaction will be evaluated as necessary.

(2) Analysis for effectiveness evaluation

The clinical response rate in terms of the clinical effectiveness will be set as the primary effectiveness endpoint. The number of patients with "effective" and its proportion (clinical response rate) among the clinically-evaluable analysis set, and its 95% confidence interval will be calculated. The number of patients with eradication or presumed eradication, and its proportion (eradication rate) among the microbiological analysis set, and its 95% confidence interval will be calculated. The clinical response rate for each disease and its 95% confidence interval, and the eradication rate and its 95% confidence interval will be calculated. Also, an exploratory analysis on the factors affecting the effectiveness will be performed as necessary.

$$\text{Clinical response rate (\%)} = \frac{\text{Number of patients with "effective"} }{\text{Number of clinically-evaluable patients excluding "indeterminate"} } \times 100$$

$$\text{Eradication rate (\%)} = \frac{\text{Number of patients with "eradication" + "presumed eradication"} }{\text{Number of patients in the microbiological analysis set excluding "indeterminate"} } \times 100$$

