3. INTERIM AND FINAL ANALYSIS

In this Study, interim analyses for periodic safety update report will be performed periodically. At the time of interim analyses, only the analyses of items necessary for periodic safety update report among the statistical analyses specified in this plan will be performed. In addition, the final analysis for the application for reexamination will be performed. At the time of the final analysis, all analyses specified in this plan will be performed.

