4. HYPOTHESES AND DECISION RULES

4.1. Statistical Hypotheses

Because this Study is not a confirmatory investigation, the tests are considered as exploratory tests.

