4.2. Statistical Decision Rules

Not applicable.

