8.2.4.5. Exploratory Analysis

For rationales for the assessment of clinical response, the number and proportion of patients will be calculated by diagnosis, clinical response (effective/not effective) and for each rationale.

Furthermore, an additional analysis may be performed as necessary. The exploratory analysis will be reported only when results providing an important interpretation are obtained.

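### The SAP reports additional, unplanned exploratory analyses only if their results are judged important, with no criterion for importance and no record of what else was run

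*SAP*

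**What the plan says.** The rule appears twice in the operative text of the SAP.

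- **Safety, SAP 8.2.3.5.** "Additional exploratory analysis may be performed, as necessary". The next sentence says that, of these, "only those that resulted in important interpretations will be reported".
- **Effectiveness, SAP 8.2.4.5.** The section opens with a planned tabulation of the reasons given for each clinical response rating, by diagnosis and response. It then allows further analysis if needed and closes: "The exploratory analysis will be reported only when results providing an important interpretation are obtained".

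Four other places bear on it.

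- SAP 4.1: "Because this Study is not a confirmatory investigation, the tests are considered as exploratory tests".
- SAP 4.2, on decision rules: "Not applicable".
- SAP 3: "At the time of the final analysis, all analyses specified in this plan will be performed".
- Protocol 7.7, on effectiveness: "an exploratory analysis on the factors affecting the effectiveness will be performed as necessary". It makes a similar provision for factors affecting adverse reactions. In neither case does it make reporting depend on the result.

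**The concern.** Exploratory findings can be weighed only if the reader knows how many analyses they were picked from. Here the choice of what to report is made after the result is known, against a standard that the SAP does not state. A factor that appears in the report as an unplanned finding may be the only one tried or one of many, and the report need not say which. The loss runs the other way too: an added analysis that found nothing may be reassuring on safety, yet nothing obliges the sponsor to show it.

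The results have uses beyond description. Under Protocol 5 they feed proper-use information and the re-examination application. Protocol 10 allows publication. Protocol 15 says that a suggested safety or effectiveness problem should prompt consideration of a package insert amendment or a new study. A chance association reported without its denominator could be given more weight than it deserves.

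**Working it through.** The plan gives no figure on this point, so the check is mainly a comparison of texts.

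**1. Which analyses does the rule cover?** In SAP 8.2.3.5 the rule refers back to the additional analyses in the sentence before it. Planned safety output lies outside it: SAP 8.2.3.1 and 8.2.3.2 tabulate adverse reactions and events, SAP 8.2.3.4 tabulates adverse reactions for every Section 5.4 factor, and SAP 9 fixes the listings. Planned effectiveness output is fixed in SAP 8.2.4.1 to 8.2.4.4. SAP 3 requires all specified analyses to be performed at the final analysis.

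**2. Is the scope equally clear for effectiveness?** Not quite. In SAP 8.2.4.5 a planned tabulation and the optional extra analysis stand under one heading, and the closing rule speaks of the exploratory analysis without limiting it to the extra part. The natural reading is that it covers only the extra part. The wider reading would make a planned table reportable only if it proved interesting, which sits badly with SAP 3.

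**3. Is the criterion defined?** No. Neither section says what makes an interpretation important or who decides, and SAP 4.2 supplies no decision rule. SAP 8.2.3.4 is a useful contrast. It also makes some output depend on a result, since system organ class and preferred term tables by factor are produced when the risk ratio is ≥2 or ≤0.5. There, however, the threshold is written down, and the overall proportion is tabulated for every factor regardless.

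**4. Is the denominator disclosed elsewhere?** No. The SAP 9 listings cover patients, events, test results and exposure. No section asks for a list or count of analyses performed.

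**5. Illustration of why the denominator matters.** Assumptions, none of them in the documents: *k* independent comparisons, no true effect in any, each judged at a two-sided 5% level.

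P(at least one nominal finding) = 1 − 0.95^k

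| k | Calculation | Probability | Expected number (0.05 × k) |
|---|---|---|---|
| 1 | 1 − 0.95 | 5% | 0.05 |
| 5 | 1 − 0.95^5 | 23% | 0.25 |
| 10 | 1 − 0.95^10 | 40% | 0.5 |
| 20 | 1 − 0.95^20 | 64% | 1.0 |
| 40 | 1 − 0.95^40 | 87% | 2.0 |

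This is ordinary multiplicity. It does not measure the effect of the reporting rule, and the probabilities would be the same if every analysis were listed. Listing gives the reader *k*, and so the means to judge a single reported finding.

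**The case against.** The strongest reply is that little is at stake. The study is a single-arm drug use investigation, SAP 4.1 disclaims any confirmatory aim, and Protocol 7.9 already names the lack of a control group and possible confounding as limitations. No primary endpoint, planned table or planned subgroup depends on the rule. For the factors that the plan names, SAP 5.4 and Appendix 2 tell the reader what was to be examined. All of this stands. It limits the point to optional extra analyses and keeps it minor.

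Three stronger readings are tempting, and the documents do not support them.

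- *That null results are removed by design.* The filter is importance, not statistical significance. A finding of no excess of central nervous system disorder in a risk group could well count as important. What can be said is that null results may go unreported and that nothing would show it.
- *That Appendix 2 lets factors be added once the data have been seen.* It says that exploratory factors might be added and fixes the reference category for any absent/present factor. It says nothing about timing.
- *That the rule reaches every exploratory analysis in the study.* SAP 4.1 calls all the tests exploratory, but the rule in SAP 8.2.3.5 is tied to additional analyses only.

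The percentages are also open to challenge. The number of comparisons and their independence are assumed. An added analysis need not be a comparison with an interval at all: the one that SAP 8.2.4.5 describes is a table of counts and proportions. For planned safety factors, SAP 8.2.3.4 withholds risk ratios when fewer than 10 patients have adverse reactions, and whether that limit would apply to added factors is not stated.

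The exploratory label does not answer what remains. It is a reason to disclose how many analyses were run, because no error control protects the reader.

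**Conclusion.** The point holds for additional, unplanned analyses of safety and effectiveness. Their reporting depends on their results, the standard for importance is undefined, and the analyses left out need not be disclosed. This is a selective rule as written, not just a missing detail. There is a secondary ambiguity in SAP 8.2.4.5 over whether the planned tabulation of reasons is covered.

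The severity is minor. The effect on the report cannot be quantified, because the SAP gives no number of additional analyses. The 40% and 64% figures are a generic illustration for an assumed 10 or 20 independent null comparisons. The conclusion rests on the wording of the two sections and on the absence of any disclosure requirement elsewhere, and does not depend on those figures.

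**What to change.** Replace the reporting sentence in both SAP 8.2.3.5 and SAP 8.2.4.5 with:

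*All additional exploratory analyses performed will be listed in the report, labelled as not prespecified, with their results (estimates and 95% CIs where calculated); those considered important will be discussed in the text.*

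In SAP 8.2.4.5 also add:

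*The table of reasons behind the clinical response ratings is always reported.*

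The cost is two reworded sentences, one added sentence and a longer report appendix. No new data are needed, no planned analysis changes, and the sponsor stays free to explore and to choose what to discuss.
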